## **CLINICAL ADVISORY BOARD**

The role of the clinical advisory board is:

- to validate the objectives and methodology of the study
- to participate in creating the protocol, the study questionnaires and/or the study analysis and publication plans
- to review the results and analyses reports

A clinical advisory board (CAB) to the Pregnancy Registry for Eurartesim™ will be recruited from HCPs participating in the Registry and specialists in teratology, with changing participation over time. Initially, this CAB will be constituted by select local country Key Opinion Leaders (KOLs) who will act as a scientific advisory board to review and provide guidance on the study procedures. After initiation of the study, this group will meet annually to provide guidance on study conduct and review the study results to date.

## 1. List of Abbreviations

ACT	Artemisinin-based Combination Therapy
AE	Adverse Events
BMI	Body Mass Index
CAB	Clinical Advisory Board
CDISC	Clinical Data Interchange Standards Consortium
COF	Contact Order Form
CRA	Clinical Research Associate
CRF	Case Report Form
DHA	Dihydroartemisinin
DSS	Demographic Surveillance System
EC	Ethics Committee
EMA	European Medicines Agency
ENTIS	European Network of Teratology Information Services
ERA	Epidemiologic Research Associate
EUROCAT	European Surveillance Network of Congenital Anomalies
EUROCRAN	European Collaboration of Craniofacial Anomalies
GP	General Practitioner

#### Protocol N° 3351 CONFIDENTIAL

- HCP Healthcare Provider
- KOL Key Opinion Leader
- MedDRA Medical Dictionary for Regulatory Activities
- MMV Medicines for Malaria Venture
- OB/GYN Obstetrician/Gynaecologist
- PQP Piperaquine
- R-M EU REGISTRAT-MAPI Europe
- SAE Serious Adverse Events

## 2. Summary

Title of the study	Pregnancy Registry for Eurartesim ™				
Study design	A European multi-centre pregnancy Registry for patients exposed to Eurartesim ™ whilst pregnant.				
Study objectives	
 
The primary objective of this study is to assess the live bir incidence of minor and major congenital birth defects followin exposure to Eurartesim™ whilst pregnant or in the one (1) month (3 days) prior to conception.
 
				
	
 
The secondary objective of this study is to assess both maternal and fetal outcome following exposure to Eurartesim™ whilst pregnant or in the one (1) month (30 days) prior to conception.
 
				
Methodology	The Eurartesim ™ Registry is open to enrolment for all women with malaria who have been exposed to Eurartesim ™ whilst pregnant.				
	Initially, HCPs known to treat and follow-up malaria patients will be invited to collaborate. A recruitment mail containing the study summary and a reply form will be sent to the HCPs. Non-respondent HCPs will be contacted by phone. Women who are not part of one of the selected sites will be able to contact their HCP who will contact Sigma-Tau on their behalf in order to be included in the Registry. In addition, all patients with pregnancies reported to the company as spontaneous events by HCPs will also be asked to participate in the Pregnancy Registry.				
	
 
The HCP will include all patients meeting the inclusion criteria and agreeing to take part in the Registry. During this recruitment phase, and for each patient, the HCP will:
 
Explain the Registry to the patient (in particular the objective of the Registry and its observational nature), give her a patient information sheet, a Consent Form and a Contact Order Form and ask the patient to read, fill in and sign them to confirm her agreement,
 
Fill in the enrolment CRF of the registry,
 
Send by fax or mail the completed Contact Order Form to the unit in charge of the patient follow-up.
 
				

	both the methor and her infant. The biological father will also be
	requested to give consent for the release of data referring to him; if the mother consents to participate in the registry but the biological father doesn't, then the mother and her infant will still be included in the registry but no data will be collected on the biological father.
	For non-included patients meeting the selection criteria, the HCP will collect few data in a short form (patient log) of the Registry.
	During follow-up visits/contacts, the HCP will: - Fill in the follow-up CRF of the registry.
	Data collection for all patients will be performed at enrolment, 4 weeks post-enrolment, 4 weeks pre-delivery, at delivery and 6 weeks post-delivery. Infants will be assessed at 6 weeks, 14 weeks and 12 months.
Clinical advisory board	A clinical advisory board (CAB) to the Pregnancy Registry for Eurartesim ™ will be recruited from HCPs participating in the Registry, with changing participation over time. Initially, this CAB will be constituted by select local country KOLs who will act as a scientific advisory board to review and provide guidance on the study procedures. After initiation of the study, this group will meet annually to provide guidance on study conduct and review the study results to date.
Sample size estimate	Data for this pregnancy registry will be regularly collected until the sample size of 376 patients required to detect a 2-fold or greater increase relative to the expected background rate of all birth defects and spontaneous abortions is reached. The Registry will be closed to new entries once this number of women with validated follow-up information has been reached and in agreement with the EMA. The following sample size is derived to detect a clinically significant difference (i.e. a >2x increase in the outcome of concern) relative to expected background rates. The assumed background risk of all reported birth defects is 23.719 per 1,000 births (EUROCAT, 2009) and the background rate of spontaneous abortion is 85.6 per 1,000 (Tata et al , 2005). Thus, assuming 80% power, 0.05 significance level (one-sided) and a loss to follow-up rate of 5%, we would require 376 pregnant women exposed to Eurartesim TM in order to be able to detect a 2-fold or greater increase in birth defects and a 1.5-fold or greater incidence in spontaneous abortions with a one-group test.

Number of HCPs	A total of 57 sites, represented across Belgium, France, Germany, Italy, The Netherlands, Spain and the UK, will be enrolled in order to recruit 376 patients over 5 years.					
Countries	7 European countries; Belgium, France, Germany, Italy, The Netherlands, Spain, UK					
Selection criteria	Inclusion Criteria:					
	The following patients will be included in the study:					
	- Women;					
	
 
who have received Eurartesim™ for malaria whilst pregnant, within one (1) month (30 days) before or at any time after conception, or
 
					
	
 
whose partner (the biological father) has received any formulation of Eurartesim™ for malaria within one (1) month (30 days) prior to conception (Committee for Medicinal Products for Human Use, 2005), and
 
					
	
 
who have been informed and agree to participate in this study.
 
					
Exclusion Criteria:						
	The following patients must not be included in the study:					
	
 
Women who refuse to participate.
 
Women participating in a clinical trial at the time of inclusion in the study.
 
					
Data collection	The following data will be collected from the HCP:					
	HCP enrolment form:					
	- Specialty.					
	- Years in practice.					
	- Geographic location.					
	- Institution type.					
	- Number of pregnant malaria patients currently treating.					
	At enrolment visit:					
	- Date of the visit.					

 
Socio-demographic characteristics of the mother (ethr [based on the standard definitions of ethnicity used in th country where the woman is enrolled in the Registry], country
 
						

	of birth, primary language and socio-economic status [based on current or most recent occupation and years of formal education]).
-	Socio-demographic characteristics of the biological father (age and current or most recent occupation).
-	Mother's lifestyle data (height [cm] and weight [kg], radiation exposure, smoking status [never/past/current], alcohol consumption [weekly units], recreational drug use.
-	Mother's malaria history (date of malaria diagnosis, date of most recent Eurartesim ™ administration and dose, previous Eurartesim ™ administrations, other treatment taken for malaria).
-	Pregnancy data (date the pregnancy was registered).
-	Estimated date of delivery/date of last menstrual period.
-	Previous or concurrent maternal complications.
-	Health status of the fetus, if it is already known at time of enrolment, i.e. via ultrasound.
-	Pregnancy outcome, if already known at time of enrolment.
-	Obstetrical history (number of previous pregnancies and outcome).
-	Significant medical history of the mother and the biological father.
-	Concomitant medication use in the mother and the biological father in the one (1) month (30 days) prior to conception.
4-weeks date:	post-enrolment and 4-weeks prior to expected due
-	Date of the visit.
-	Serious adverse events (drug related or not) in the mother since previous visit/contact.
-	Exacerbation of pre-existent clinical condition in the mother since previous visit/contact.

-	Comorbidities in the mother since previous visit/contact.
-	Concomitant medication use in the mother since previous visit/contact.
-	Maternal complications since previous visit/contact.
-	Fetal complications since previous visit/contact; any spontaneous abortions ( $\leq 28$ weeks gestation), elective abortions, ectopic pregnancies, late fetal or neonatal deaths (>20 weeks gestation), premature deliveries ( $\leq 37$ completed weeks).
At end of	pregnancy:
-	Date of the end of pregnancy.
-	Maternal complications since previous visit/contact.
-	Maternal mortality.
-	Stillbirth (>28 weeks gestation).
-	Early neonatal mortality.
-	Gestational age at delivery (estimated from the last menstrual period).
-	Live births.
-	Infant birth weight (adjusted for gestational age).
-	Infant major and minor birth defects (primary outcome of interest).
-	Serious adverse events (drug related or not) in the mother or the infant since previous visit/contact.
-	Exacerbation of pre-existent clinical condition in the mother since previous visit/contact.
-	Comorbidities in the mother since previous visit/contact.
-	Concomitant medication use in the mother since previous visit/contact.

	6 weeks after end of pregnancy:
	- Date of the visit.
	- Maternal complications since previous visit/contact.
	- Maternal mortality.
	- Early neonatal mortality ( $\leq 7$ days of birth).
	- Neonatal mortality ( $\leq$ 28 days of birth).
	- Infant major and minor birth defects.
	
 
Serious adverse events (drug related or not) in the mother or the infant since previous visit/contact.
 

	14 weeks after end of pregnancy:
	- Date of the visit.
	- Maternal complications since previous visit/contact.
	- Maternal mortality.
	- Infant mortality.
	
 
Serious adverse events (drug related or not) in the mother or the infant since previous visit/contact.
 

	- Infant development.
	12 months after end of pregnancy:
	- Date of the visit.
	
 
Serious adverse events (drug related or not) in the mother or the infant since previous visit/contact.
 

	- Infant development.
Statistical Analysis	Statistical analyses will be carried out using SAS software version 9.2.
	REGISTRAT-MAPI EU will prepare a statistical analysis plan to be reviewed by Sigma-Tau and the CAB.
	At regular intervals tables and listings will be produced to enable

reporting of key interim outcomes to regulatory authorities, participating HCPs and the scientific/medical community at large.

Reporting of data (other than individual reports concerning individual patients or participating HCPs to those individual participants), will be in aggregate form to ensure individual patient and HCP confidentiality.

All analyses, primary and secondary, will be conducted in two manners; on all women and by stratifying the women depending on whether they were directly exposed to EurartesimTM or whether the biological father was exposed to EurartesimTM.

### Primary analysis

In accordance with the primary objectives of the study and the way the study was powered, the main focus of the statistical analysis will be estimation of the incidences of birth defects and spontaneous abortion. 95% confidence intervals will be computed around these incidences in order to judge whether there is an increase of these incidences as compared to background risks.

In order to control for potential confounders, birth defects and spontaneous abortion will be described according to parameters such as concomitant infections/diseases and medication use.

For spontaneous abortions, women who discontinued the study prior to delivery will not be taken into account in the primary analysis. A sensitivity analysis will be performed considering all patients, assuming that women who discontinued the study prior to delivery had experienced spontaneous abortion; this will provide us with the highest estimation of incidence of spontaneous abortion (i.e. the worst-case scenario).

In the same way, in the primary analysis, incidences of birth defects will be analysed without considering patients who discontinued the study prior to 14 weeks after the end of pregnancy. A sensitivity analysis will be performed on all patients assuming that women who discontinued the study prior to 14 weeks after the end of pregnancy had experienced birth defects.

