#### Pregnancy-related information

Frequency and type of pregnancy outcome will be stratified by the earliest trimester of exposure, demographics and medical background characteristics. Gestational weeks will be counted from the date of the last menstrual period, with the second trimester as beginning at week 14 and the third trimester as beginning at week 28. Women who discontinued the study prior to delivery will not be taken into account in the primary analysis. A sensitivity analysis of patients who did not complete the entire follow-up will be performed, in the same manner as described in the 'Primary analysis' section above.

Time-to-event variables will be analysed via survival analysis methods (e.g. Kaplan-Meier survival estimates and associated confidence intervals).

In order to control for potential confounders, pregnancy outcomes will be analysed according to parameters such as lifestyle factors, concomitant infections/diseases and medication use. Patient's Body Mass Index (BMI) will be calculated from the patient's height (cm) and weight (kg) data.

In order to optimize patient recruitment, patients with recurring malaria and Eurartesim™ use during pregnancy will be included in this pregnancy Registry in addition to first malaria infections. However, first and

	recurring malaria infections will be analyzed separately due to the					
	potential differences in disease aetiology and pregnancy outcomes.					
	Analytical methods					
	Continuous variables will be d	described by their mean, standard				
	deviation, median, quartiles 1 and 3, extreme values (minimum an					
	maximum) and the number of missing data.					
	Categorical variables will be described by the total and percentage of					
	each response method and the number of missing data.					
	Continuous variables will be compared using Student's t-test (2 groups)					
	or variance analysis (>2 groups)	. If the conditions for applying these				
	tests are not met (normality, h	omoscedasticity), the Mann-Whitney,				
	Wilcoxon (2 groups) or Kruskal-Wallis (>2 groups) non-parametric tests will be used.					
	Categorical variables will be compared between subgroups using the					
	Chi-2 test if the theoretical total of each class studied is greater than 5.					
	Otherwise Fisher's exact test will be used.					
	The ordinal variables will be compared between subgroups using a					
	Cochran-Mantel-Haenszel test.					

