In a further study, Rijken *et al* (2008) treated 50 pregnant women with recurrent Plasmodium falciparum infections (despite 7 day treatments with quinine or artesunate (+/- clindamycin) or both) with DHA-PQP. The gestational age at DHA-PQP treatment was 23.7±8.2 (9.2–39.1) weeks. 45 of the women had a known pregnancy outcome. Two infants were reported to be abnormal at birth; one with a small umbilical hernia (exposed to treatment at 24 weeks) and one diagnosed clinically with Patau syndrome (trisomy 13) (exposed to treatment at 34 weeks), who subsequently died at 6 hours of age. The remaining infants were all observed at 1 month of age and found to be healthy. The two abnormalities identified in the newborns are unlikely to be drug related. Thus, DHA-PQP was effective and well tolerated and there was no evidence of toxicity for the mothers or the newborns.

The phase four trial, or post-marketing phase, where the drugs are already in use on the markets, seeks to examine the risks and benefits of the new drug in different and larger segments of the population. This phase is important because it examines issues such as the longer-term effects of drug exposure on larger populations. Post-marketing surveillance is also important because even the most well designed phase three studies might not uncover every problem that could become apparent once a product is widely used. Furthermore, the new product might be more widely used by groups that might not have been well studied in the clinical trials and there might be reports of adverse drug reactions once a drug becomes available on the open market (African Media and Malaria Research Network, 2010).

This epidemiologic surveillance registry is necessary because of the potential for exposure in the first trimester of pregnancy and the unknown risks in pregnancy for any new chemical entity. The current lack of data regarding Eurartesim™ use during pregnancy makes such a registry an essential component of the ongoing assessment of

the safety of Eurartesim™. Through the registry, patients exposed to any formulation of Eurartesim™ during pregnancy will be registered by healthcare providers (HCPs), the pregnancies followed and the outcomes ascertained through follow-up. This information will be used to detect any potential risks to pregnant women and/or teratogenic effects in pregnancies exposed to any formulation of Eurartesim™.

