#### 26/06/2012 Version - 12.0

#### **TABLE 1: STUDY FLOW CHART**

Assessment by HCPs	Visit 1 (Enrolment)	Visit 2 (4 weeks post- enrolment)	Visit 3 (4 weeks prior to expected due date)	Visit 4 (end of pregnancy)	Visit 5 (6 weeks after end of pregnancy)	Visit 6 (14 weeks after end of pregnancy)	Visit 7 (12 months after end of pregnancy)
Date of the visit	x	x	x	x	x	x	x
Socio-demographic characteristics	x *						
Lifestyle data	x						
Malaria history	x						
Date of exposure to Eurartesim ™	x						
Pregnancy data and obstetrical history	x						
Maternal complications	x	x	x	x	x	x	
Fetal complications	x	x	x	x			
Concomitant medication use	x *	x	x	x			
Significant medical history	x*						
Exacerbation of pre-existent clinical condition		x	x	x			
Comorbidities		x	x	x			
AEs/SAEs		x	x	x	x	x	X
Maternal mortality				x	x	x	
Infant mortality				x	x	x	
Infant development					x	x	X

\*These data will also be collected for the biological father.

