#### Primary analysis

In accordance with the primary objectives of the study and the way the study was powered, the main focus of the statistical analysis will be estimation of the incidences of birth defects and spontaneous abortion. 95% confidence intervals will be computed around these incidences in order to judge whether there is an increase of these incidences as compared to background risks.

In order to control for potential confounders, birth defects and spontaneous abortion will be described according to parameters such as concomitant infections/diseases and medication use. For spontaneous abortions, women who discontinued the study prior to delivery will not be taken into account in the primary analysis. A sensitivity analysis will be performed considering all patients, assuming that women who discontinued the study prior to delivery had experienced spontaneous abortion; this will provide us with the highest estimation of incidence of spontaneous abortion (i.e. the worst-case scenario).

In the same way, in the primary analysis, incidences of birth defects will be analysed without considering patients who discontinued the study prior to 14 weeks after the end of pregnancy. A sensitivity analysis will be performed on all patients assuming that women who discontinued the study prior to 14 weeks after the end of pregnancy had experienced birth defects.

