#### Secondary outcomes:

- Maternal complications.
- Maternal mortality (up to 6 weeks post-delivery).
- Spontaneous abortions (≤28 weeks gestation).
- Elective abortions.
- Ectopic pregnancies.
- Stillbirth (>28 weeks gestation).
- Premature deliveries ( $\leq$ 37 completed weeks).
- Early neonatal mortality ( $\leq 7$  days of birth).
- Neonatal mortality ( $\leq 28$  days of birth).
- Gestational age at delivery (estimated from the last menstrual period).
- Low birth weight (adjusted for gestational age).
- Infant development.

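### Spontaneous abortion ends at 28 weeks by definition, but dropout for it is judged at delivery, so known non-events leave the primary denominator and are counted as events in the sensitivity analysis

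*Protocol*

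**What the plan says.** Protocol Section 7.4.1 lists "Spontaneous abortions (≤28 weeks gestation") and, as a separate outcome, "Stillbirth (>28 weeks gestation"). The Summary and Section 5.5 use the same 28-week limit.

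The primary analysis text, in the Summary and again in Section 5.7, uses a different time point. It first excludes: "For spontaneous abortions, women who discontinued the study prior to delivery will not be taken into account in the primary analysis". The sensitivity analysis then takes all patients, "assuming that women who discontinued the study prior to delivery had experienced spontaneous abortion", and the protocol says that "this will provide us with the highest estimation of incidence of spontaneous abortion (i.e. the worst-case scenario"). Neither place makes an exception for gestational age at the last contact.

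For birth defects, the same text leaves out women who discontinued before 14 weeks after the end of pregnancy, then assumes in the sensitivity analysis that they had birth defects. Sections 4 and 7.4.1 define that outcome as an incidence among live births.

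The flow chart includes "Visit 3 (4 weeks prior to expected due date"). Section 5.5 collects the date of the last menstrual period or the estimated delivery date at enrolment, and Section 5.7 counts gestation from the last menstrual period.

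**The concern.** Under the protocol's own definitions, a woman's spontaneous-abortion status is settled once she is known to be pregnant after week 28. A later loss is a stillbirth. The analysis rule keeps the question open until delivery.

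Take a woman enrolled at week 20, seen still pregnant at Visit 3 and then lost. The registry holds proof that she did not have the event. She is excluded from the primary incidence as if her status were unknown, and the sensitivity analysis then assigns her the one outcome her record rules out.

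A worst case should assign the event wherever it remains possible. This rule also assigns it where it is impossible, so its result can lie above the true upper bound. Section 5.7 judges an increase by setting the 95% confidence interval against the background risk, so an overstated bound can suggest a signal that the data cannot contain. The birth-defect rule has a smaller, related gap: it does not say that a documented pregnancy without live birth stays out of the imputation.

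**Working it through.** **Inputs**
- Sample size 376, loss to follow-up 5%, background spontaneous-abortion rate 85.6 per 1,000 (8.56%): Section 5.4.
- Event window up to 28 weeks: Section 7.4.1.
- Share of dropouts documented past 28 weeks: not given, so varied from none to all.
- Confidence interval method: not named. Wilson is used, with exact (Clopper–Pearson) as a check.
- Assumptions: the true rate equals background, and all 376 women were enrolled by week 28.

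**The plan's own figure.** An exact one-sided binomial test for a doubling of birth defects needs 357 women, and 357/0.95 = 375.8, which rounds up to 376. The split used below, 357 followed and 19 lost, therefore agrees with the plan's sample size. (The normal approximation named in Section 5.4 gives 346 after the allowance for loss. That is a separate matter.)

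**Step 1. Counts.** Lost before delivery: 376 × 0.05 = 18.8, so 19. Followed: 376 − 19 = 357. Events at background: 357 × 0.0856 = 30.6, so 31.

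**Step 2. Rule as written.** Primary: 31/357 = 8.7%. Sensitivity: (31 + 19)/376 = 50/376 = 13.3%, which is 1.55 times background. Wilson 95% CI 10.2–17.1%, exact 10.0–17.2%. The estimate lies above the 1.5-fold level used for sizing (1.5 × 8.56% = 12.84%), although the assumed rate is background.

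**Step 3. Status judged at 28 weeks.** Let k be the number of the 19 documented as pregnant past 28 weeks. Sensitivity = (50 − k)/376. Primary = 31/(357 + k).

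| k of 19 | Sensitivity | Wilson 95% CI | Includes 8.56%? | Primary |
|---|---|---|---|---|
| 0 | 50/376 = 13.3% | 10.2–17.1% | no | 31/357 = 8.7% |
| 6 | 44/376 = 11.7% | 8.8–15.3% | no | 31/363 = 8.5% |
| 9 | 41/376 = 10.9% | 8.1–14.5% | yes | 31/366 = 8.5% |
| 19 | 31/376 = 8.2% | 5.9–11.5% | yes | 31/376 = 8.2% |

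The exact interval agrees on inclusion in the two middle rows: 8.6–15.4% for 44/376 (lower limit 8.63%) and 7.9–14.5% for 41/376. The smallest count whose lower limit exceeds 8.56% is 43 by Wilson and 44 by the exact method. The interval therefore starts to include background at k = 8 (Wilson) or k = 7 (exact).

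**Step 4. Where 6 and 9 come from.** For an earlier cohort of 50 treated women, Section 3 reports: "The gestational age at DHA-PQP treatment was 23.7±8.2 (9.2–39.1) weeks". If timing were normal, 1 − Φ((28 − 23.7)/8.2) = 30% would be past 28 weeks at treatment, and 1 − Φ((24 − 23.7)/8.2) = 49% would be past 28 weeks four weeks later. Of 19 women these shares are 5.7 and 9.2. They serve only as points on the range. The first in particular describes women already past 28 weeks at treatment, who would fall outside the risk set if they were also enrolled then.

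**Step 5. Can the affected women exist?** Section 5.2 admits exposure at any time after conception. Visit 3 falls at about week 36 if the due date is week 40 (an assumption). A woman who attends Visit 3 and leaves before delivery is exactly the case described.

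**The case against.** The strongest reply is that this is one sensitivity analysis, openly labelled as a worst case, that errs in the cautious direction for a safety registry, and that the primary estimate hardly moves. The last part stands: 8.7% against 8.5% at k = 6 or 9. The label does not save the rule, because a worst case should stop at what is possible.

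A second reply is that the change in conclusion depends on an assumed share. That stands too. At 6 of 19 the interval still excludes background. The cohort in Section 3 is a weak guide, being 50 women given rescue treatment for recurrent infection, whereas this registry also takes pre-conception and paternal exposure. Active tracing (Section 5.5) should also reduce the number of women seen at Visit 3 whose outcome stays unknown.

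Four stronger readings are tempting, and the protocol does not support them:
- **That the excess over background comes only from women who cannot have had the event.** At k = 9, the other 10 imputed women could have had it. Much of the excess belongs to any worst-case imputation and remains after the fix.
- **That women with a known pregnancy outcome who leave before 12 months are also imputed.** The pregnancy-related text does say "A sensitivity analysis of patients who did not complete the entire follow-up will be performed", but in the same manner as the primary analysis, which most naturally carries over that section's cut-offs. Section 5.7 also limits it to the main outcomes.
- **That this is the only protection against loss to follow-up.** The protocol also provides tracing, confirmation through treating clinicians and recorded reasons for loss.
- **That women first enrolled after 28 weeks should count as non-events.** They were never at risk of the event under observation, and keeping them would dilute the incidence.

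**Conclusion.** The point holds in a limited form. The stated rule misclassifies women enrolled by week 28 who are documented as pregnant after it and then discontinue before delivery. Each is wrongly absent from the primary denominator and wrongly present in the sensitivity numerator, so the reported upper bound exceeds the attainable one whenever there is at least one such woman.

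Each such woman adds 1/376, about 0.27 percentage points, to the sensitivity estimate. With 19 lost and background incidence in the rest, the result as written is 13.3%, and the attainable worst case lies between 13.3% (none past 28 weeks) and 8.2% (all past 28 weeks). Whether the comparison with background changes cannot be settled from the protocol, which gives no gestation at dropout. The logical error does not depend on that share. The effect on the primary estimate is small and upward.

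For birth defects the conclusion is narrower. A live-birth incidence should not impute a defect to a documented pregnancy without live birth, and the text does not say so. A reader might infer that the rule certainly does impute these women. The protocol does not establish that, since a documented loss may fall outside a live-birth analysis altogether. The wording needs clarifying, and no size is claimed.

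**What to change.** In the primary analysis text of both the Summary and Section 5.7:

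1. Judge spontaneous-abortion status at 28 weeks instead of at delivery.
2. Keep women enrolled by 28 weeks and documented as pregnant beyond 28 weeks as non-events in both the primary and the sensitivity analysis.
3. In the sensitivity analysis, impute the event only for discontinued women last known to be pregnant at 28 weeks or earlier.
4. Leave women first enrolled after 28 weeks out of the spontaneous-abortion risk set, counting them neither as events nor as non-events.
5. For birth defects, state that the sensitivity analysis does not impute a defect for a documented pregnancy without live birth.

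The cost is a wording amendment in two places. The dating information and visit dates needed are already collected, so no further patients, visits or data are required.
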